10.1.2 CT perfusion (CTP) images

Using a high-pressure injector, 50 mL of iodixanol (Visipaque, 370 mg/mL) is rapidly injected through the cubital vein at 8 mL/s. The injection is completed simultaneously with the continuous scanning of a selected single layer for 50 s. A head-fixing strap is used to secure the patient during scanning. Cerebral perfusion parameters are transmitted to specialized perfusion CT software (Revolution, GE Healthcare, USA) for manual post-processing. The perfusion parameters, including cerebral blood volume (CBV), CBF, time to peak (TTP), and mean transit time (MTT), are measured by post-processing software (Advantage Workstation 4.7, Revolution, GE Healthcare, USA).

Cranial CTP images are conducted at admission and day 7. The area around the marginal hematoma is selected as the region of interest (ROI), and the symmetrical area in the opposite hemisphere is regarded as the contralateral mirror ROI. The CBF, CBV, MTT, and TTP are assessed in both the area around the hematoma and the contralateral mirror area.

10.2 Clinical scale

10.2.1 Modified Rankin Scale (mRS)

The mRS reflects disability at follow-up time, which consists of seven disability levels, ranging from 0 (no symptoms) to 5 (severe disability) and 6 (death). We intend to assess the mRS on days 90 after randomization.

10.2.2 Barthel index (BI)

The BI represents functional status at follow-up time, the scores of which range from 0 (complete dependence) to 100 (complete independence) measured by several items, including feeding, bathing, grooming, dressing, bowels, bladder, toilet use, transfers, and stairs. We intend to assess the BI on days 90 after randomization.

10.2.3 National Institute of Health Stroke Scale (NIHSS)

The NIHSS is commonly used to evaluate neurological deficits in stroke and comprises five items in 11 fields of different neurological statuses (scores range from 0–42, representing normal to severe neurological deficits). The NIHSS is scored at admission, 3-day, 7-day and 14-day after randomization during hospitalization.

10.2.4 Glasgow Coma Scale (GCS)

GCS is a practical method for the evaluation of impairment of conscious level in response to defined

stimuli, which contains three parts, including eye-opening, verbal response, and motor response (scores range from 3–15, representing deep coma to normal). The GCS is scored at admission, 3-day, 7-day and 14-day after randomization during hospitalization.

11. Outcomes

11.1 Efficacy outcomes

11.1.1 Primary outcome

Primary efficacy is independence at 90 days, as scored using the mRS, and dichotomized as a good (score 0-3) or a poor outcome (score 4-6), following the Cochrane analysis of thrombolysis in stroke. The proportion of patients in each arm with good outcomes is compared at 90 days.

11.1.2 Secondary outcomes

- (1) mRS distribution at 90 days.
- (2) BI scores at 90 days.
- (3) NIHSS scores at 3, 7 and 14 days.
- (4) GCS scores at 3, 7 and 14 days.
- (5) Hematoma volumes, clearance rate and reduction volume at 3, 7, 14 day.
- (6) Absolute PHE volumes, clearance rate and reduction volume at 3, 7, 14 day.
- (7) Relative PHE volumes, clearance rate and reduction volume at 3, 7, 14 day.
- (8) CBF, CBV, MTT, and TTP at 7 days.

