11.2 Safety outcomes

The 7-day oxygen pressure (PO₂), the 7-day carbon dioxide pressure (PCO₂) and the 7-day PH value, as well as the death rate and the complication rate (including hematoma expansion, pulmonary infections, acid-base imbalances and so forth) during hospitalization.

12. Study Flow Diagram

13. Study Periods

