15.2 Statistical methods

The modified intention-to-treat analysis of efficacy outcomes and safety outcomes were performed on the full analysis set, which was composed of all patients who received randomization independent of treatment and at least 1 efficacy evaluation after enrollment. The χ^2 test was used in the unadjusted analysis. A modified Poisson regression model with robust error estimation was used to analyze the primary outcome and other dichotomous endpoints, with adjustment for prespecified covariates (age, male and onset-to-needle time). Relative risk (RR) with a 95% confidence interval (CI) was calculated in both unadjusted and adjusted analyses. Generalized linear models (GLMs) were used to analyze continuous endpoints, including NIHSS scores, Barthel scale scores, and hematoma and edema volumes. The distribution of mRS was analyzed using an ordinal logistic regression model, and odds ratios (OR) with 95% CI were calculated. Post hoc subgroup analysis was performed for the primary outcome according to age, sex, and baseline NIHSS scores, with an OR of 95% CI. No interim analyses were performed.

A 2-sided P value <.05 is considered statistical significance. Because multiple comparisons potentially cause type I error, findings for secondary outcome analyses should be interpreted as exploratory. SPSS software (version 26, IBM) and R software (version 4.1.0) are used for the statistical analyses.

16. Data Management

The enrolled participants were entered in the case report form (CRF) by the evaluator within 24 hours and entered in the electronic form within 3 days. All of the entered personnel signed on the CRF. The assessors were blinded to allocation information. A data supervisor who was not involved in clinical research is set up for data verification. Two investigators who blinded to allocation information rechecked the original data, and if the data was found to be wrong, the data should be corrected in time. The data of modification and the person who modified it should be recorded to ensure that the data is correct.

17. Data and Security Monitoring Board (DSMB)

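### Barthel, NIHSS and, by implication, GCS are compared by GLM with no rule for deaths, so by default these are comparisons among survivors and can favour the arm with more deaths

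*Combined protocol and SAP*

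**What the plan says.** - **Endpoints.** Section 11.1.2 lists "BI scores at 90 days", "NIHSS scores at 3, 7 and 14 days" and "GCS scores at 3, 7 and 14 days" among the secondary outcomes.
- **Model.** Section 15.2 states: "Generalized linear models (GLMs) were used to analyze continuous endpoints, including NIHSS scores, Barthel scale scores, and hematoma and edema volumes". GCS is not named and comes under this sentence only because the list is open.
- **Scales.** Section 10.2.2 defines the Barthel index (BI) from "0 (complete dependence) to 100 (complete independence" points. Sections 10.2.3 and 10.2.4 give NIHSS 0-42 and GCS 3-15. None has a level for death. Only the mRS has one: section 10.2.1 describes it as "ranging from 0 (no symptoms) to 5 (severe disability) and 6 (death".
- **Analysis set.** The full analysis set in section 15.2 needs randomization and one efficacy evaluation after enrollment. A patient assessed at day 3 who dies later therefore belongs to it.
- **Deaths.** The primary outcome counts mRS 4-6 as poor (11.1.1), and section 11.2 lists "the death rate and the complication rate" as safety outcomes, limited to the hospital stay. No expected mortality is given.
- **Missing values.** No section gives a score, a composite, an imputation rule or any other method for a patient with no BI, NIHSS or GCS value at a visit, whether from death or from another cause.

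**The concern.** A GLM needs a response value. If nothing is specified, a patient who has died contributes nothing to the day-90 BI mean or to later NIHSS and GCS means. Under section 13.3 the mRS and the BI come from the same 90-day telephone follow-up. The same death is then a 6 on one scale and absent from the other, so the two functional outcomes describe different sets of patients.

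Survival is itself affected by what happens after randomization. Suppose one arm loses more of its most severe patients. Its survivors are then a milder group, and their mean looks better. The bias can run either way: it could hide a benefit of NBO that keeps severe patients alive, or hide a harm. At stake is whether the functional and neurological secondary outcomes can be read as supporting the mRS result.

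**Working it through.** The plan has no figure of its own on this point, so there is nothing to reproduce. The check asks how far a survivor mean can move. Every mortality rate and score distribution below is an assumption; only the scale ranges and the 48 patients per arm come from the documents.

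**1. Closed form, strongest link.** Let the BI be uniform on 0-100, the same in both arms, and let the lowest-scoring fraction d die.

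- Mean among survivors: 50(1 + d).
- Mean with deaths scored 0: 50(1 - d²).

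| Deaths, control v NBO | Survivors, NBO minus control | Deaths scored 0, NBO minus control |
|---|---|---|
| 10% v 4% | 52.0 - 55.0 = -3.0 | 49.92 - 49.50 = +0.42 |
| 15% v 5% | 52.5 - 57.5 = -5.0 | 49.875 - 48.875 = +1.0 |
| 20% v 10% | 55.0 - 60.0 = -5.0 | 49.5 - 48.0 = +1.5 |

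The arm with fewer deaths looks worse among survivors, and the sign changes once deaths are scored.

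**2. Weaker link, all three scales.** This is a simulation with 400,000 patients per arm. Both arms have the same underlying normal score, rounded and cut to the scale range: BI mean 65, SD 28; NIHSS mean 9, SD 5; GCS mean 13, SD 2. The arms differ only in mortality. The correlation between survival and underlying score is 0.7. Entries are the higher-mortality arm minus the lower-mortality arm, first among survivors, then with deaths at the worst score (BI 0, NIHSS 42, GCS 3).

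| Mortality, lower v higher | BI | NIHSS (higher is worse) | GCS |
|---|---|---|---|
| 2% v 6% | +1.5; -1.2 | -0.3; +1.1 | +0.1; -0.3 |
| 5% v 15% | +3.0; -4.0 | -0.6; +2.8 | +0.2; -0.8 |
| 10% v 20% | +2.8; -4.6 | -0.5; +3.0 | +0.2; -0.9 |

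Among survivors, all three scales favour the arm with more deaths. For NIHSS and GCS that shift is only a few tenths of a point.

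**3. No link.** With correlation 0, the BI difference among survivors lies between -0.06 and +0.01 in every mortality scenario run. The deaths are then ignored without distorting the comparison of survivors.

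**4. Equal mortality.** In step 1, equal d in both arms gives a difference of 0 on either method.

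**5. One arm of 48.** Take BI 10 in 8 patients, 60 in 20 and 90 in 20. The mean is 3,080/48 = 64.2. If six of the eight worst die, the survivor mean is 3,020/42 = 71.9, and with deaths scored 0 it is 3,020/48 = 62.9.

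**6. Against sampling error.** A uniform BI has SD 100/√12 = 28.9. With 48 per arm the standard error of a difference is about 28.9 × √(2/48) = 5.9. The -3.0 in step 1 is about half of that, and 10% v 4% is about 5 v 2 deaths.

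**The case against.** A reader might infer that the plan excludes patients who die, or that these outcomes are not analysed by intention to treat. The documents say neither. Section 15.2 declares a modified intention-to-treat set and names a model; the restriction to survivors follows only from its silence.

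The size is also open to challenge. Eligibility in section 7.2 (hematoma 10-30 mL, GCS above 8, no life-threatening condition) may keep deaths few. The closed-form example makes the lowest scorers die with certainty, and its shift is within sampling error. NIHSS and GCS stop at day 14, so only earlier deaths affect them. Death already enters function through the primary outcome and through the mRS distribution, which is analysed by ordinal logistic regression. Section 15.2 calls the secondary findings exploratory. Withdrawal and loss to follow-up leave the same gap as death. Finally, section 15.1 shows that enrolment is over, so replacing the stated GLM now would be a post hoc change.

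Most of this stands. It limits the size of the point and argues for adding to the GLM rather than replacing it. It does not close the gap. The exploratory label is there because of multiple comparisons; it does not address a comparison whose direction may be wrong. No rule tells a reader how a dead patient was treated in the BI analysis.

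**Conclusion.** The point holds as a gap in specification with a foreseeable direction of bias. As written, the BI comparison at day 90 and the NIHSS and GCS comparisons at each visit are by default comparisons among survivors. They favour the arm with more deaths when two conditions are met: mortality differs between arms, and deaths fall among patients who would have scored badly.

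The size cannot be fixed from the documents. For BI, the assumed scenarios give survivor shifts of about 1.5 to 5 points when death and score are linked, and about zero when they are unrelated or when deaths are balanced. For NIHSS and GCS the shifts are small (0.3 to 0.6 and 0.1 to 0.2 points at correlation 0.7).

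A reader might go further and conclude that the trial's secondary results do point the wrong way. That is not supported: the documents report no deaths by arm and no BI, NIHSS or GCS results. The primary outcome and the mRS distribution are unaffected. The matter should be corrected, but no main conclusion depends on it.

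**What to change.** In section 15.2:

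1. Keep the GLM and label it as a comparison among survivors with an observed score.
2. Add a rank-based or ordinal analysis of BI at day 90, and of NIHSS and GCS at days 3, 7 and 14, with death ranked below every living score. Label it a composite of death and function. Ranking avoids tying a death with a living patient at BI 0.
3. Report deaths and numbers analysed by arm at each visit, up to day 90 for BI, because the safety death rate in section 11.2 covers only the hospital stay. Show other causes of missing scores separately, since ranking deaths does not deal with withdrawal or loss.
4. Disclose the added analysis as post hoc, because enrolment has ended.

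The cost is some SAP wording, a recode and one extra analysis per endpoint. Deaths up to day 90 should already be recorded through the mRS. The downside is that the added estimate mixes death and function and must be read as such.

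### The CT perfusion outcome gives no role to the admission scan or the mirror region, so it is under-specified and probably less precise than the collected data allow

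*Combined protocol and SAP*

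**What the plan says.** Section 11.1.2, item (8), gives the outcome as "CBF, CBV, MTT, and TTP at 7 days". It names no region, no contrast between regions and no use of an earlier scan.

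Section 10.1.2 describes what is collected. On timing: "Cranial CTP images are conducted at admission and day 7". On regions: "The CBF, CBV, MTT, and TTP are assessed in both the area around the hematoma and the contralateral mirror area", where "the symmetrical area in the opposite hemisphere is regarded as the contralateral mirror ROI". Each patient with both scans therefore has four values of each parameter: two regions at two times. The trial flow chart in section 8 puts the first CTP in the enrollment column, before allocation.

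Section 15.2 gives the analysis: "Generalized linear models (GLMs) were used to analyze continuous endpoints, including NIHSS scores, Barthel scale scores, and hematoma and edema volumes". Perfusion is not among the examples, and no covariates are named for these models. The one adjustment set in the section, "with adjustment for prespecified covariates (age, male and onset-to-needle time", is attached to the primary and other dichotomous endpoints and contains no perfusion value. The same section says that "findings for secondary outcome analyses should be interpreted as exploratory".

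**The concern.** Two of the measurements that the trial pays for have no stated use. The admission perfusion value is a pre-treatment measurement of the same quantity in the same patient, usually the most useful covariate for a day-7 comparison. The mirror region is an obvious within-patient reference. If outcome (8) is analysed as listed, both drop out.

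The gap stands out beside the other imaging outcomes. Section 10.1.1 defines reduction and clearance of hematoma and edema against baseline, and items (5) to (7) of section 11.1.2 use those definitions. Item (8) has no counterpart.

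Two things are at stake. One is precision in a trial that ended with 96 patients (section 15.1). The other is clarity. A perihematomal value, a mirror value, a ratio or a difference, each with or without the admission scan, would all be compatible with the text for each of the four parameters. These answer different questions.

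**Working it through.** **No figure to reproduce.** The documents give no SD, expected effect, correlation or power for perfusion. The sample size in section 15.1 concerns the 90-day mRS only. The sizes below therefore rest on assumed correlations, shown as a range.

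**Inputs from the documents.** 48 patients per arm (section 15.1), and two-sided testing at 0.05: "A 2-sided P value <.05 is considered statistical significance" (section 15.2). For illustration, power is set at 80% and every patient is taken to have both scans.

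**Step 1: unadjusted day-7 value.** In units of the between-patient SD, the standard error of the arm difference is sqrt(2/48) = 0.204. The difference detectable with 80% power is (1.960 + 0.842) × 0.204 = 0.57 SD. For an assumed true effect of 0.5 SD, power is Φ(0.5/0.204 − 1.960) = Φ(0.49) = 69%.

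**Step 2: adjusted for the admission value.** If r is the within-arm correlation between the admission and day-7 perihematomal values, adjustment multiplies the variance by 1 − r². The detectable difference becomes 0.572 × sqrt(1 − r²).

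| r (assumed) | variance factor 1 − r² | detectable difference | power at 0.5 SD |
|---|---|---|---|
| 0.3 | 0.91 | 0.55 SD | 73% |
| 0.5 | 0.75 | 0.50 SD | 81% |
| 0.7 | 0.51 | 0.41 SD | 93% |
| 0.9 | 0.19 | 0.25 SD | >99% |

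The factor never exceeds 1. If r were zero, the loss would be one residual degree of freedom out of 96 − 2 = 94.

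**Step 3: side-to-side contrast at day 7.** With equal SDs in the two regions and correlation ρ between them in one scan, perihematomal minus mirror has variance factor 2(1 − ρ).

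| ρ (assumed) | variance factor 2(1 − ρ) | detectable difference | power at 0.5 SD |
|---|---|---|---|
| 0.3 | 1.40 | 0.68 SD | 54% |
| 0.5 | 1.00 | 0.57 SD | 69% |
| 0.7 | 0.60 | 0.44 SD | 89% |
| 0.9 | 0.20 | 0.26 SD | >99% |

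The contrast beats the raw value only if ρ exceeds 0.5. Below that it is worse.

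**Step 4: if oxygen also acts on the mirror side.** Suppose the mirror carries half of a 0.5 SD effect and ρ = 0.7. The contrast then estimates 0.5 × (1 − 0.5) = 0.25 SD, with standard error 0.204 × sqrt(0.60) = 0.158. Power is Φ(0.25/0.158 − 1.960) = Φ(−0.38) = 35%, against 69% for the raw value. Entering the day-7 mirror as a covariate gives 61%, also below 69%, because it too removes part of the effect. Admission values precede treatment and do not have this problem.

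**The case against.** The strongest reply is that silence is not a choice. Item (8) does not say that absolute perihematomal values alone will be compared, and section 15.2 does not say that the mirror or the admission scan will be left out. That stands: a reader might infer a decision to analyse raw day-7 values, but the text supports only that the endpoint is under-specified.

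A reader might also infer that differences between patients, or across the whole brain, drown any perihematomal effect. The documents give no perfusion SD, effect or correlation that could show this. Randomization balances such differences in expectation, so they cost precision and not validity. Nor can it be said that a comparison of perihematomal values fails to target the tissue of interest, because section 10.1.2 defines that region.

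A third tempting step is to make the mirror contrast the outcome and claim the gain of the favourable rows in step 3, a variance factor of 0.60 or 0.20. Those figures depend on an assumed ρ and on a comparator that ignores the admission scan. The contrast is also a different estimand. Inhaled oxygen is systemic, and an effect shared by both hemispheres would cancel.

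Finally, the outcome is the last of eight secondary outcomes and is declared exploratory. This limits the consequence, but it does not remove the need to say what is estimated. None of these replies gives a reason to leave the admission value unused.

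**Conclusion.** The point holds as an improvement available at no cost in data, not as an error that threatens the trial's conclusions. Outcome (8) names neither its region nor its reference, and the plan gives no role to the admission CTP or the mirror region although both are collected. The analysis is therefore probably less precise than it could be. Under assumed admission-to-day-7 correlations from 0.3 to 0.9, adjustment would lower the detectable difference from 0.57 SD to between 0.55 and 0.25 SD. Where in that range the trial lies cannot be said from the documents. The range assumes a linear model with a common slope in both arms and complete scans in 48 patients per arm; fewer scans would raise all the figures.

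The stronger conclusion, that the day-7 side-to-side contrast should replace the perihematomal value, does not follow. That contrast can gain or lose precision and removes any common effect, so it belongs beside the main comparison. The primary outcome is not affected.

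**What to change.** In section 11.1.2, define item (8) as the day-7 value of each parameter in the perihematomal region. In section 15.2, name perfusion among the continuous endpoints and compare arms in the GLM with the admission perihematomal value of the same parameter as covariate. The admission mirror value may be added, since it too is measured at admission.

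As supplementary analyses, to help separate local from whole-brain effects, report:

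- the arm difference in the day-7 mirror values;
- the side-to-side contrast at day 7, as log(perihematomal/mirror) for CBF and CBV and as perihematomal minus mirror for MTT and TTP, adjusted for the same contrast at admission.

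State with the contrast that it is more precise than the raw value only if the correlation between regions exceeds 0.5, and that it cancels any effect common to both hemispheres.

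The cost is wording and a few model runs; no new scans or measurements are needed. Because enrolment has ended, and section 15.1 reports that imaging results had been seen by then, label the definition as made after enrolment. Keep the outcome secondary and exploratory.

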11.2 Safety outcomes

The 7-day oxygen pressure (PO₂), the 7-day carbon dioxide pressure (PCO₂) and the 7-day PH value, as well as the death rate and the complication rate (including hematoma expansion, pulmonary infections, acid-base imbalances and so forth) during hospitalization.

12. Study Flow Diagram

13. Study Periods

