7.3 Follow-up time point

All included patients are followed-up at baseline, 3 days, 7 days, 14 days and 90 days after randomization, respectively.

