7.4 Randomization and blinding

All patients are enrolled consecutively and randomized in 1:1 ratio to receive 8 L/min flow of 100% O_2 via oxygen storage face mask or 2 L/min flow of 100% O_2 via nasal catheter using a computer-generated randomization code. This is an open label trial, so we adopt a partial blinding strategy where the clinical assessors are blinded to the treatment allocation but the operators are not. That is, the neurological functional scores and imaging tests are assessed by investigators blinded to the

intervention and grouping. The operators responsible for oxygen interventions to the patients are unblinded.

	STUDY PROTOCOL					
	Enrollment	Allocation		Foll	ow-up	
TIMEPOINT	0 day	0 day	3 days	7 days	14 days	90 days
ENROLLMENT						
Eligibility screen	Х					
Informed consent	Х					
Allocation		Х				
INTERVENTIONS						
NBO		←		\longrightarrow		
Control		←		\longrightarrow		
ASSESSMENTS						
Personal data		Х				
Safety evaluation				Х		
NIHSS	Х		Х	Х	Х	
Glasgow Coma Scale	х		Х	Х	Х	
Barthel index						Х
mRS						Х
Cranial CT	Х		Х	Х	Х	
CT perfusion	Х			Х		

8. Trial Flow Chart

NBO, normobaric hyperoxia; CT, computed tomography; NIHSS, National Institute of Health Stroke Scale; mRS, modified Rankin Scale.

9. Interventions

All patients within 24 hours from definite onset time are screened by the cranial CT to confirm ICH at admission. After diagnosis of ICH, the patient or his certigiers will decide whether to participate in this

trial. If they agree, an informed consent will be signed, and allocation will proceed.

Participants will be allocated into two arms:

The NBO group, undergoing high-flow oxygen via oxygen storage face masks (100% O₂, flow rate 8 L/min, 1 hour, four times daily, and 2 L/min via nasal catheter during intermittent periods, for 7 days) immediately in the emergency room after randomization.

The control group, undergoing 2 L/min flow of 100% O₂ via nasal catheter in the emergency room after randomization, for 24 hours daily for 7 days.

Secondary stroke prevention follows the 2022 AHA/ASA guidelines for the diagnosis and treatment of acute intracerebral hemorrhage. All participants are hospitalized for at least 14 days, and if the hematoma expands and causes cerebral hernia, hematoma aspiration or a decompressive craniectomy will be conducted.

10. Measurements

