10.1 Imaging test

10.1.1 Non-contrast cranial CT image

Non-contrast head CT scans are performed to assess the severity of hematoma and perihematomal edema (PHE). A 256-slice CT scanner is used following standard local protocols. Next, 5-mm-thick CT images are measured for hematoma and PHE volumes using the General Electric Company workstation built-in image software. All volume measurements are performed using a semi-automated process involving tracking the perimeter of appropriately high- and low-attenuation areas and calculating the lesion area for each slice multiplied by the slice thickness to obtain the lesion volume. Independent analysis of all images is performed by two doctors blinded to the treatment assignment, and any discrepancies are resolved consensually.

Cranial CT scans are performed at admission, day 3, 7, and 14. Software from United Imaging (United Imaging Healthcare Co., Ltd., Shanghai, China) is used for the automated calculation of hematoma and absolute PHE volumes. The relative PHE is calculated by dividing the absolute PHE volume by the baseline hematoma volume to obtain a dimensionless ratio. The reduction volumes of the hematoma, absolute PHE, and relative PHE follow the defined formula: baseline volume – follow-up volume. Besides, the clearance rate of the hematoma, absolute PHE and relative PHE are calculated as a percentage using the defined formula: $100\% \times (baseline volume - follow-up)$

volume)/baseline volume.

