13.3 Follow-up periods

Neurological measurements including mRS score and Barthel index are assessed via a telephone interview at 90 days.

14. Adverse events monitoring

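### Deaths and complications are counted to discharge, so events after day 14 are compared over unequal follow-up; fixed windows to day 14 and day 90 can be built from data already planned

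*Combined protocol and SAP*

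**What the plan says.** - Section 11.2 fixes the blood gas measures at one day: "The 7-day oxygen pressure (PO₂), the 7-day carbon dioxide pressure (PCO₂) and the 7-day PH value". It then lists "the death rate and the complication rate (including hematoma expansion, pulmonary infections, acid-base imbalances and so forth) during hospitalization", with no end day.
- Section 9 gives the only statement on length of stay: "All participants are hospitalized for at least 14 days". There is no upper limit.
- The schedule in section 8 has a row "Safety evaluation" with a single mark, in the day-7 column.
- Section 14.1 asks for adverse events to be recorded both while the intervention runs and afterwards, and followed to resolution. It names no last day for counting them.
- Fixed time points already exist. Section 7.3: "All included patients are followed-up at baseline, 3 days, 7 days, 14 days and 90 days after randomization". Section 10.1.1: "Cranial CT scans are performed at admission, day 3, 7, and 14". Section 10.2.1 makes death level 6 of the mRS at day 90. Section 13.3 says that the mRS and Barthel index "are assessed via a telephone interview at 90 days".

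**The concern.** Every efficacy outcome in section 11.1 is tied to a day counted from randomization. Deaths and complications are tied to discharge, which happens after randomization. Discharge can reflect recovery, and it can reflect decisions by staff who know the allocation: section 7.4 leaves the operators unblinded. If one arm goes home sooner, it is observed for less time and shows fewer in-hospital events even when the daily risk is the same. If that arm were the NBO arm, the treatment would look safer than it is. Deaths after discharge also fall outside the safety death rate.

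Numbers are small. Section 15.1 reports 48 patients per arm, so one event is 1/48 = 2.1 percentage points, and a few late events can alter the picture.

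**Working it through.** The plan gives no figure for this window, so there is nothing to reproduce. The check has two parts.

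**Which events are exposed to unequal time?**

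1. All surviving patients still under follow-up are in hospital to day 14 (section 9). Up to that day the windows are equal.
2. Hematoma expansion is found on CT, and the last scheduled CT is on day 14 (section 10.1.1).
3. Acid-base status rests on blood sampling, and the only scheduled sample after baseline is on day 7 (section 13.2).
4. Unscheduled tests could add later cases of both. Pulmonary infection and death depend less on a scheduled test and are the outcomes most open to unequal time.

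**How large could the distortion be?**

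Assumptions, none taken from the documents: the true hazard is equal in both arms; the 14-day risk R is 10%, 20% or 30%; every patient in one arm leaves on day 14; every patient in the other leaves on day L = 16, 18, 21 or 28.

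- Daily hazard to day 14: h = −ln(1 − R)/14. For R = 20%, h = 0.2231/14 = 0.0159.
- Constant hazard: risk to day L = 1 − exp(−hL).
- Hazard falling to a quarter after day 14: risk to day L = 1 − exp(−14h − (h/4)(L − 14)).
- Spurious risk ratio = R / risk to day L. The true ratio is 1.00.

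Worked case, R = 20%, L = 21:

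- Constant hazard: 1 − exp(−0.0159 × 21) = 28.4%; ratio 20/28.4 = 0.70. In 48 patients per arm that is 9.6 v 13.6 expected events.
- Falling hazard: 1 − exp(−0.2231 − 0.0159/4 × 7) = 22.2%; ratio 20/22.2 = 0.90, or 9.6 v 10.7 expected events.

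Range over R = 10% to 30%:

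| Stay in the longer arm | Ratio, constant hazard | Ratio, quarter hazard after day 14 |
|---|---|---|
| 14 days | 1.00 | 1.00 |
| 16 days | 0.88–0.90 | 0.97 |
| 18 days | 0.79–0.82 | 0.94 |
| 21 days | 0.68–0.72 | 0.89–0.91 |
| 28 days | 0.53–0.59 | 0.81–0.83 |

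If the longer stay were in the other arm, the ratio would be inverted. With a window closed at day 14 in both arms, equal hazards give 1.00 whatever the discharge dates.

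**The case against.** The strongest reply is that the 14-day minimum already protects most of the comparison. Complications that occur early fall in the common period, and two of the three named complications have no scheduled test after day 14. The larger distortions in the table also need an extreme pattern: because 14 days is a minimum, an average stay of 14 means essentially every surviving patient in that arm leaves on that day. This stands. It limits the likely size but does not remove the defect for pulmonary infection and death.

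Three stronger readings are tempting, and the documents do not support them.

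- A reader might infer from the schedule that safety is assessed only on day 7. Section 14.1 describes recording beyond the intervention period, and the day-7 mark may simply reflect the day-7 blood gases. What can be said is that the schedule, section 11.2 and section 14.1 describe safety observation differently and are not reconciled.
- A reader might infer that deaths after discharge are lost. Section 11.1.2 lists the 90-day mRS distribution, which includes death. A lower in-hospital figure is a different window and not a contradiction.
- A reader might infer that the comparison is known to favour NBO. Without length-of-stay data, neither a difference in stay nor its direction is shown.

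It can also be said that a new window is a late change. Section 15.1 describes enrolment as finished at 96 patients, so replacing the stated outcome outright would be a post hoc change. That stands too, and it is why the in-hospital rates should be kept and the added analysis labelled. A day-14 label alone would not equalize observation either: section 7.2.3 withdraws patients for reasons that overlap with safety events, and for a decision to operate.

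**Conclusion.** The concern holds in a limited form. The in-hospital window is not the same length for every patient, and nothing in the plan prevents it from differing by arm. The part at risk is what happens after day 14, mainly pulmonary infection and death. The size is unknown. On the assumptions above, the spurious ratio lies between 0.53 and 0.90 with a constant hazard and between 0.81 and 0.97 with a hazard that falls to a quarter, and there is none if stays are equal. If most complications come early, or stays are similar, the effect is modest. The primary outcome is not affected. The point merits a change because a better-defined comparison can be made from observations the plan already schedules.

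**What to change.** - Make the main between-arm safety comparison complications from randomization through day 14, and all-cause death through day 14 and through day 90. Take day-90 deaths from mRS 6, and show the number of patients with unknown vital status in each arm.
- Count all randomized patients, including those withdrawn under section 7.2.3. State this explicitly, because section 15.2 analyses safety on a set that requires at least one efficacy evaluation after enrolment.
- Keep the in-hospital rates of section 11.2 as description, together with length of stay by arm.
- If the fixed-window analysis was added after enrolment, label it so.
- Reconcile the single day-7 safety mark in section 8 with sections 11.2 and 14.1, and state the last day on which adverse events are counted.

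The cost is wording and re-tabulation of dated inpatient events, the scheduled CT scans and the 90-day mRS; no visit is added. There are two downsides. Complications after day 14 leave the main rate and have to be listed separately. Day-90 vital status depends on the telephone follow-up, and section 15.1 allows for 10% loss. Complications to day 90 are not proposed, because the call is described only for the mRS and Barthel index.
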